## 9.3 Sample for analysis

We will study the following range of patients:

- Intention to treat (ITT) population: this is the sample of randomized patients, regardless of whether they are followed up using telehealth or not
- Per-protocol (PP) population: this is the sub-sample of the ITT population that follows the study protocol during the entire follow-up period (12-18 months)
- Safety population: this is the subset of the ITT population that begins follow-up (uses telehealth), and either completes follow-up or withdraws from the study.

The analysis will mainly be carried out using the ITT population. The reason for this is that loss-to-follow-up is likely to bias the results so that we estimate a greater effect of the use of telehealth than what is estimated by focusing on the PP population. Thus, an analysis of the ITT population is a more conservative estimate.

In addition, we will carry out analyses where we compare the outcome of the intervention group with one or more registry-based control groups. The control groups can be selected based on discretionary assessments and / or by means of statistical methods, e.g. propensity score matching. It will be possible to base the choice of control group on variables such as gender, age, diagnosis and municipality of residence. The results of such an analysis will have to be interpreted with caution but will constitute an interesting supplement to the rest of the analysis.

## 9.4 Statistical analysis

The aim of the trial is to estimate the effects of telehealth on the three outcomes of health status, patient experience and resource use in the health service. The choice of statistical method for analyzing the data will be adapted to the characteristics of the outcome variables in question.

### Non-parametric methods

For several variables, both from registers and from the surveys, we will use non-parametric tests such as Wilcoxon signed ranks test or McNemar test. In these tests, each of the collected variables is examined separately, and the null hypothesis is that there is no difference between the intervention and control group. This null hypothesis could be rejected if the individual test's test observer is above critical limit. We will use the conventional significance level of 5% in the statistical analyses. For the analyses of variables where we utilize the randomization of intervention and control group, statistically significant differences between the groups could have interpretation as causal effects.

For parts of the data material, information will only be available for the participants in the intervention group. This applies to information that is directly related to receiving telehealth. In these cases, we will investigate whether there are changes in outcomes over time. The choice of statistical method could be the same as for other analyses. Significant changes will usually be interpreted as significant associations, but care will be taken to interpret any findings as causal effects.

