## Protocol synopsis

Title of the study	A pragmatic randomized control trial comparing telehealth with standard clinical care in the follow-up of patients with chronic conditions
Short title	Pragmatic RCT of telehealth vs standard care in follow-up of patients with chronic conditions
Treatment	
Control treatment	Standard clinical care
Study centers planned	The following six municipalities are included in the study: Oslo, Eid, Kristiansand (recruiting from the Agder counties), Ullensaker (in cooperation with Gjerdum), Larvik and Bodø
Study period	
First patient recruited: February 19th, 2019
 
Anticipated recruitment period: February 1st, 2019 to June 30th, 2020
 
Estimated date of last patient completed: June 30th, 2021

Treatment duration	
Patients in the intervention group will be followed up using telehealth solutions for 12 – 18 months
 
Patients in the control group receive standard clinical care throughout the study period

Study objectives	
Primary:
 
 
1. To assess whether patients who are followed up using telehealth experience an improved health state (or lower reduction in health state for patients with deteriorating health) compared to patients receiving standard clinical care.
 
2. To assess whether patients who are followed up using telehealth are more satisfied with the health care services than patients receiving standard clinical care.
 
3. To assess whether patients who are followed up using telehealth utilize less healthcare resources than patients receiving standard clinical care
 
 
Exploratory:
 
 
1. To evaluate the organization of the service
 
2. To evaluate the cost-effectiveness of telehealth compared to standard clinical care
 

Study endpoints	
Primary endpoints:
 
 
• Health related quality of life (EQ-5D)
 
• Overall satisfaction with treatment and follow-up
 
• Health and care cost per person
 
 
Secondary endpoints:
 
 
• Physical functioning
 
• Sleep
 
• Coping
 

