## **6.3 Use of health and care services**

The use of health and care services is analyzed using information from various national registers. Health and care services include all kinds of services from primary and specialist health care providers. The use of health and care services is registered for all participants in the period 2017-2022. Thus, the use of health and care services can be followed at least two years before and up to three years after recruitment.

Use and costs are calculated on a yearly basis from recruitment.

The following outcomes are analyzed:

- The number of consultations with the GP
- Contact with the follow-up service
- Number of visits to the home service
- Scope and composition of home-based care services
- Number and scope of municipal emergency unit (KAD) stays
- Number of contacts with emergency services
- Number and composition of outpatient consultations and day treatments
- Number, scope and composition of hospital admissions and bedtime
- Number of emergency admissions due to complication of chronic disease
- Number and composition of consultations with private specialists
- Scope and composition of drug use

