### **Total health and care cost per person**

Total costs for health and care services per person are calculated on a yearly basis using publicly available statistics of cost related to the use of health and care services and actual use of health and care services. Total costs are also split between different parts of the health service (primary and specialist health care services).

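### No estimator is assigned to the primary cost endpoint; a rank test is permitted, and neither a mean-cost analysis nor adjustment for pre-recruitment cost is tied to it

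*Combined protocol and SAP*

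**What the plan says.** The synopsis and Table 1 list "Health and care cost per person" as the primary endpoint for the third objective: "To assess whether patients who are followed up using telehealth utilize less healthcare resources than patients receiving standard clinical care".

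Section 6.3 defines the quantity but not its analysis. It says "Total costs for health and care services per person are calculated on a yearly basis using publicly available statistics of cost", multiplied by actual use. On timing it says "Use and costs are calculated on a yearly basis from recruitment", without stating which year is the primary one. On history it says "the use of health and care services can be followed at least two years before and up to three years after recruitment".

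Section 9.4 opens by leaving the method to the characteristics of each outcome. Its non-parametric part says "For several variables, both from registers and from the surveys, we will use non-parametric tests", giving the Wilcoxon signed-rank and McNemar tests as examples and 5% as the significance level. Its parametric part plans regression for some variables or groups of variables, says that difference-in-difference and structural equation models will be applied, and mentions resource use as one group that might be modelled jointly. Neither part names cost. Section 9.4 also foresees control variables in sensitivity analyses, without listing them.

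**The concern.** A primary endpoint should come with an effect measure, a model and a covariate set. Cost has none of these, so a rank test, a difference-in-difference model or a joint structural model would all comply with the plan, and the choice could be made after the data are seen.

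The choice matters more for cost than for most outcomes. Whether telehealth uses fewer resources, and whether it pays in the cost-benefit analysis of section 6.5, depends on mean cost per person, because a mean multiplies up to a budget. A rank test asks a different question: whether a telehealth patient tends to cost more or less than a control patient. With skewed cost the two can disagree. The intervention makes this plausible. Section 4.1 gives every telehealth user monitoring and nurse contact, and section 6.3 lists follow-up-service contact among the use outcomes, while the hoped-for saving lies in fewer deteriorations and admissions. Higher typical cost with a thinner upper tail is the pattern in which ranks and means part company. Skew is also the usual argument for choosing a rank test under a rule that looks to the outcome's characteristics.

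Precision is the second issue. Pre-recruitment cost is available and is likely to predict later cost, but the plan does not say that it enters the cost analysis, or how.

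**Working it through.** **The plan's own figures.** Table 7 has no row for cost. The nearest is panel D, emergency inpatient days, mean 4.14 (SD 12.43). With a two-sided 5% level and 80% power, n per arm = 2(1.960 + 0.842)² × SD² / difference². For a difference of 2.00 this is 2 × 7.849 × 12.43² / 2.00² ≈ 606.3, so 607 after rounding up (Table 7: 606). Eleven of the 12 rows reproduce to within one patient per arm. The exception, VAS 0.105 (81 computed, 87 stated), has no bearing here. The power calculations are therefore about differences in means. At the planned 300 per arm, power for a 2-day difference is 50%.

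**Skew.** SD divided by mean is 12.43/4.14 = 3.0 for emergency days, 4.15/2.34 = 1.8 for outpatient consultations and 15.21/14.66 = 1.0 for GP consultations.

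**Can ranks contradict means?** The documents give no cost distribution, so every cost model below is an assumption. Each uses 300 per arm, 1,500 simulated trials and a two-sided 5% level. The two-sample Wilcoxon test is used because the arms are independent; the signed-rank test named in the plan is for paired data.

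*Model 1, lognormal cost, true mean 10% lower with telehealth.*

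| CV, control / telehealth | Rank test declares telehealth costlier |
|---|---|
| 1 / 1 and 3 / 3 | about 0% |
| 2 / 1.5 | 21% |
| 1.5 / 1 | 39% |
| 3 / 2 | 56% |
| 2 / 1 and 3 / 1.5 | 98% |

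A Welch test on means wrongly declares telehealth costlier in at most 1.6%.

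*Model 2, a fixed amount added for every telehealth patient and fewer admissions; mean cost 120 in control and 110 with telehealth.* The rank test declares telehealth costlier in 10% (+10, admissions 30% to 20%), 60% (+20, 30% to 15%) and 94% (+30, 30% to 10%) of trials; Welch in at most 0.2%. With nothing added and admissions cut from 30% to 20%, the rank test reverses in 0.1%.

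*Model 3, emergency days matched to panel D (zero-inflated lognormal) plus a gamma background cost with shape 1 and scale 1.5, in bed-day equivalents.* Telehealth cuts days by 30% and adds 0.5 of contact for everyone. The true saving is 0.30 × 4.14 − 0.5 = 0.74. With 30% of patients having any days, the rank test reverses in about 79% of trials, and Welch wrongly declares telehealth costlier in 0.3%. Changing one input at a time:

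- share with any days 20% or 50%: 96% or 35–38%
- background scale 3, 5 or 10: 27–28%, 10% or 3–4%
- added contact 0.25, 0.1 or 0: 23%, 4% or under 1%
- 30% of patients with emergency days have none, instead of all stays being shortened: 43%, or 7% at background scale 3

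**Value of pre-recruitment cost.** With equal pre and post variances and correlation r, variance relative to a post-only comparison is 1 − r² with prior cost as a covariate (ANCOVA) and 2(1 − r) for difference-in-difference.

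| r (assumed) | ANCOVA | Difference-in-difference |
|---|---|---|
| 0.3 | 0.91 | 1.40 |
| 0.5 | 0.75 | 1.00 |
| 0.7 | 0.51 | 0.60 |

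At r = 0.5, ANCOVA is worth 600/0.75 = 800 patients analysed unadjusted, while difference-in-difference gains nothing.

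**The case against.** The strongest reply is that the plan already contains the right ingredients. Difference-in-difference models compare mean changes, need a pre-period, and are stated as something that will be applied. Resource use appears in the parametric part. Register data start in 2017, control variables are foreseen, and the non-parametric sentence covers several variables, which could simply be the counts of use in section 6.3.

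Most of this stands, and it rules out three stronger readings that a reader might infer. The documents do not support saying that the plan has no mean-based method, because it names one. They do not support saying that prior cost will be discarded, because the data are to be collected and silence about their role is not a decision to ignore them. They do not support saying that cost has been assigned a rank test, because it has been assigned nothing. What the reply does not supply is a sentence tying any of these ingredients to cost.

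Two further objections are fair. The reversal depends heavily on assumptions: patients are selected for high service use, so a low background cost may be unrealistic, and a higher one shrinks the effect quickly. And a mean-based analysis is no cure for low power: in the 0.74 bed-day scenario an unadjusted Welch test detects the saving in only about 10–12% of trials. An imprecise estimate of the right quantity is still preferable to a precise answer to a different question.

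**Conclusion.** The concern holds as under-specification of a primary endpoint. The plan permits a rank test on register variables and does not tie its difference-in-difference models or its pre-recruitment data to cost. A rank test would not estimate the mean cost that the third objective and the cost-benefit analysis require.

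The size of the reversal risk cannot be fixed from the documents. It is about 0% when cost shifts proportionally or no contact is added, and over 90% in some models where typical cost rises and the tail thins. It would be a mistake to take 79%, or any other single value, as the rate to expect in this trial.

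The precision argument also rests on assumed correlations, but the ordering does not: with equal pre and post variances, 1 − r² is below 2(1 − r) for every r below 1. Below r = 0.5 the only named model with a pre-period is less precise than ignoring that period. The point should be fixed before analysis; it does not invalidate the design.

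**What to change.** Add to section 9.4 that the primary analysis of cost per person is the intention-to-treat difference in arithmetic mean cost over the first year from recruitment. Pre-recruitment cost enters as a covariate (ANCOVA, not change scores), together with centre. The confidence interval is robust or bootstrap. Other mean-based models, such as a gamma model with robust errors, are acceptable alternatives provided one is named in advance as primary. State that rank tests on cost are descriptive only, and that any difference-in-difference or structural equation analysis of cost is supportive.

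The cost is a paragraph of text: section 6.3 already provides for the register data, including at least two years before recruitment. The drawback is that mean-based intervals on skewed cost will be wide. Covariate adjustment recovers part of this, and the report should give the interval rather than rely on significance.

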### **5.2 Step 2: The GP assesses eligibility**

The Norwegian Directorate of Health has planned that approximately 100 GPs will participate in the trial. The centers have signed letters of intent with GPs who are committed to recruiting patients for the trial. The GP has the medical responsibility for the patients on their list and should therefore assess the patient's eligibility for telehealth (i.e., whether the patient meets the inclusion criteria) based on their knowledge of the patient, patient records and the information in the proposal message from the project administration or other health personnel.

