#### Health-related quality of life (EQ-5D)

We focus on self-reported health status using the validated questionnaire EuroQol 5 Dimensions 5 Levels (EQ-5D-5L) which is used to measure health status and associated health-related quality of life. The form contains five dimensions of health, including walking, personal care, ability to perform common tasks, pain / discomfort and anxiety / depression. For each of these dimensions, the patients indicate a level of 1-5, which describes the degree of health problems within each dimension (no problems, some problems, moderate problems, severe problems, extreme problems). The response combination of level within each dimension allows a total of 3125 different health conditions. Research-based methods have been developed to assign a quality of life value between zero and 1.0 to each of the 3125 combinations.

We will measure patients' EQ-5D scores during follow-up. Changes in EQ-5D scores for patients in the intervention group will be compared with changes in EQ-5D scores in the control group. Telehealth is considered to improve health-related quality of life if patients in the intervention group experience a statistically significant improvement (at a 95 % confidence level), or a lower deterioration, in health-related quality of life during follow-up compared with patients in the control group.

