## 9.2 Randomization

Patients who agree to participate in the trial are randomized 1: 1 to the intervention and control group. The treatment allocation is non-blinded in that both providers and patients will know the outcome of the treatment allocation. The actual randomization is carried out by a project employee in the local centers. The project administration stores sealed randomization envelopes in their office. Each sealed envelope contains a sheet marked with either "tiltak" (intervention) or "kontroll" (control), which determines which group the patient is placed in. For each GP in the trial, there is a separate stack of six envelopes: three "intervention" and three "control". Each time a patient on GP's X's list is invited to an information meeting, the project employee takes the top envelope from GP's stack of envelopes. If more than six patients are recruited on the GP's patient list, the project employee will receive a new stack of six envelopes for this GP. Thus, we can ensure that there will be approximately equal distribution of intervention and control patients from each GP. Oslo Economics distributes the stacks of opaque envelopes to the projects.

If a patient is invited to an information meeting and the patient's GP has not previously been involved in the trial, a separate stack of envelopes for this GP should be obtained prior to the meeting so that the patient can be randomized into the trial.

For each information meeting (chapter 8.3), the project employee takes an envelope from the appropriate GP's stack *without opening it*. The envelope is opened together with the patient after the consent form is signed, and the questionnaire is filled out. If the patient does not agree to participate in the trial, the envelope remains sealed. The project employee brings the sealed envelope back to the office and puts it back in the proper stack of envelopes.

 This randomization technique was considered the best practically implementable technique given the practical implementation of the study.

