### Parametric methods

For some (groups of) variables, it will be relevant to use different types of regression models to study the effect of telehealth. Both difference-in-difference models and structural equation models will be applied. The use of structural equation models allows to study how telehealth affects a group of variables simultaneously. For example, it will be examined whether telehealth affects a group of health variables, a group of user satisfaction variables, or a group of resource use variables simultaneously. Where necessary, we will use structural equation models that consider that the outcome variables are binary / categorical and that the data material has so-called multi-level structure, since the material consists of repeated observations of the same individuals within the same municipality, over time.

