## 9.5 Analysis of loss-to-follow-up

We expect loss-to-follow-up among the participants in the ITT population, and it is important to document this in order to be able to interpret the results. Patients can drop out either before or after consent is given.

We will register anonymous information about patients who drop out before consent is given. This includes gender, age (in intervals), main diagnosis, recruitment channel, reason for non-participation.

Drop-out that occur after the consent has been obtained will be analyzed to ensure that drop-out does not drive the results. Characteristics of those who drop out will be compared to those who complete the follow-up.

Drop out will also be highlighted through interviews with GPs and other health personnel, as well as with the project administration.

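### Section 9.4 names only paired tests for comparing the two randomised arms, which are independent samples

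*Combined protocol and SAP*

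**What the plan says.** Section 9.4, under Non-parametric methods, says of several register and survey variables: "we will use non-parametric tests such as Wilcoxon signed ranks test or McNemar test". The following sentence refers to these same tests and fixes their hypothesis: "the null hypothesis is that there is no difference between the intervention and control group". The level is 5%. A causal reading of significant differences is then allowed for one set of analyses: "For the analyses of variables where we utilize the randomization of intervention and control group". A second paragraph deals separately with data held only for the intervention group, where the question is change over time.

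Section 9.2 describes individual 1:1 allocation. On its structure it says: "For each GP in the trial, there is a separate stack of six envelopes". Each stack holds three envelopes for each arm. No patient is matched to another. Section 6.1 sets out the EQ-5D comparison as one between two groups: "Changes in EQ-5D scores for patients in the intervention group will be compared with changes in EQ-5D scores in the control group". Section 9.5 adds: "We expect loss-to-follow-up among the participants in the ITT population".

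The documents name no two-sample non-parametric test (rank-sum, chi-square or Fisher).

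**The concern.** The Wilcoxon signed-rank and McNemar tests work on differences within matched pairs. The randomised arms consist of different, unmatched people. The named tests therefore do not fit the hypothesis given to them, and they could be used in only two ways:

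- **Across the arms.** Each intervention patient would have to be paired with an unrelated control. This cannot use everyone when the numbers with data differ. When the numbers agree, the result depends on which pairing is chosen.
- **Before and after, within one arm.** The plan does not state this for between-arm questions. It would test a time trend, not the effect of telehealth.

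The comparisons affected are those based on randomisation, for which the plan allows a causal interpretation. Allocation is open and two midterm reports are planned, so it is better not to leave the replacement test to be chosen after data have been seen.

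**Working it through.** **1. Which design does the plan's own power calculation assume?**
Inputs are the SDs and differences in Table 7, 80% power and 5% significance. Two-sided testing is assumed because the plan does not state sidedness. For two independent means:

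n per arm = 2 × ((1.960 + 0.842) × SD / difference)²

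For VAS with a difference of 0.05: 2 × (2.802 × 0.238 / 0.05)² = 355.7, carrying the quantiles unrounded. Table 7 prints 356.

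| Outcome (SD) | Differences | Computed per arm | Printed per arm |
|---|---|---|---|
| VAS (0.238) | 0.05 / 0.08 / 0.105 | 355.7 / 138.9 / 80.7 | 356 / 139 / 87 |
| GP consultations (15.21) | 2 / 3 / 4 | 907.9 / 403.5 / 227.0 | 908 / 404 / 227 |
| Outpatient consultations (4.15) | 0.5 / 1 / 1.5 | 1081.4 / 270.4 / 120.2 | 1081 / 270 / 120 |
| Emergency inpatient days (12.43) | 1.33 / 2 / 2.5 | 1371.1 / 606.3 / 388.1 | 1371 / 606 / 388 |

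Eleven of the 12 rows match. The exception (VAS 0.105) does not bear on this point. A paired calculation gives the same figures only if the within-pair correlation is zero. At a correlation of 0.5, the first row would need 178 pairs. Table 7 therefore treats the arms as independent.

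**2. Can a paired test be computed across the arms?**
Section 5.2 plans that "approximately 100 GPs will participate in the trial". Further assumptions are a Poisson number of patients per GP with mean 6 (600/100), stacks of 3 + 3, and 20,000 runs for each rate of missing follow-up.

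| Missing follow-up | Arms exactly equal | Median difference | 95th percentile |
|---|---|---|---|
| 0% | 3.6% | 7 | 21 |
| 10% | 3.2% | 8 | 24 |
| 20% | 2.8% | 9 | 26 |
| 30% | 3.0% | 9 | 26 |

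**3. What happens if the arms are equal?**
Assumptions: 300 per arm, normal change scores, and 2,000 runs per setting. The intervention mean change is -0.105, the decline quoted in Section 9.1. The control mean is -0.105 under the null, or -0.105 - 0.05 = -0.155 with a benefit of 0.05. The SD of change is assumed; 0.238 is the Table 7 SD, which is not labelled an SD of change.

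| SD of change | Signed-rank, null | Signed-rank, benefit | Rank-sum, benefit | Opposite verdicts from two random pairings (benefit) |
|---|---|---|---|---|
| 0.15 | 4.9% | 97.7% | 98.3% | 1.5% |
| 0.238 | 4.6% | 71.5% | 71.4% | 7.4% |
| 0.35 | 4.6% | 39.7% | 40.1% | 8.1% |

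In one simulated data set (SD 0.238, difference 0.05), the rank-sum p-value was 0.0035. Across 2,000 random pairings of those same patients, the central 95% of signed-rank p-values ran from 0.0012 to 0.0139.

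**4. Ordinal and binary items.**
- Four-point item, odds ratio 1.5, under three assumed base distributions (5/20/45/30%, 10/30/40/20% and 25% each): signed-rank power 75.0/76.2/79.8%, rank-sum 77.3/77.4/80.3%, and opposite verdicts in 4.3/4.8/2.8% of runs. Signed-rank type I error was 5.4% to 5.7%.
- Binary item, control proportion 30/50/70% and a 10-point difference: McNemar power 71.7/69.6/82.1%, chi-square 72.1/71.0/82.2%, and opposite verdicts in 2.5/2.3/1.7% of runs. McNemar type I error was 4.6% to 6.0%.

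**5. Within-arm use.**
If both arms decline by 0.105 with SD 0.238 and do not differ, the standardised mean change in one arm of 300 is 0.105 / (0.238/√300) ≈ 7.6. A signed-rank test rejected in all 1,000 simulated runs, although the stated between-arm null was true.

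**The case against.** The strongest reply is that the error would not pass unnoticed. The arms will almost never have equal numbers, so an analyst would see at once that the tests do not run. Multiplying the figures above, equal arms combined with a changed verdict would occur in about 0.028 × 0.015 = 0.04% to 0.036 × 0.081 = 0.3% of trials per variable, unless patients were dropped to force equality. Nothing in the plan proposes that. The 8% figure is therefore conditional on equal arms and is not the risk to this trial.

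The plan also offers other routes. The two tests are given only as examples, and the opening of Section 9.4 adapts the method to the outcome. The Parametric methods paragraph plans difference-in-difference and structural equation models, including for "a group of user satisfaction variables". Paired tests can suit a one-to-one matched version of the registry comparison in Section 9.3, as well as the intervention-only data. The text may simply have written signed-rank where rank-sum was meant.

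All of this limits the consequence, but it does not rescue the sentence. Both examples are of the wrong kind for the hypothesis stated next. Pairing is a feature of the design, not of the outcome variable. The intervention-only paragraph is presented as a separate case. The parametric models are planned for some variables or groups of variables, and do not supply a non-parametric test for variables examined one at a time.

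**Conclusion.** The text is wrong as written, for the non-parametric comparisons of the randomised arms only. The named tests usually cannot be computed across the arms, and when they can, they give no single answer. Type I error and power are essentially unaffected, Table 7 does not change, and no primary endpoint is shown to depend on these tests. What is lost is a reproducible, pre-specified test for the comparisons that the plan would read causally. It should be corrected before analysis.

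The mismatch itself rests on the text alone. Its size rests on the assumed GP list sizes, missing-data rates, SDs of change and response distributions.

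**What to change.** In Section 9.4, Non-parametric methods:

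- For comparisons of the randomised arms, replace the two named tests with the Wilcoxon rank-sum (Mann-Whitney) test, on values or change scores, for ordinal or skewed variables. Use the chi-square test for binary variables, or Fisher's exact test where cells are sparse.
- Keep the signed-rank and McNemar tests for within-patient change in the intervention-only data, and for any one-to-one matched registry comparison under Section 9.3.
- Optionally, since allocation is blocked within GP, stratify the two-sample tests by GP or centre. The unstratified tests are valid without this.

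The cost is a few lines of wording. No new data or patients are needed.
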